6.1.8. Data Adjustments/Handling/Conventions

All collected data will be presented in Clinical Data Interchange Standards Consortium (CDISC) datasets. Data not subject to analysis according to this plan will not appear in any tables or graphs but will be included only in the CDISC datasets.

All *P* values will be displayed in 4 decimals and rounded using standard scientific notation (e.g., 0.XXXX). If a *P* value less than 0.0001 occurs it will be shown in tables as <0.0001; similarly, if a *P* value greater than 0.9999 occurs it will be shown in tables as >0.9999.

Adverse events will be coded using the Medical Dictionary for Regulatory Activities (MedDRA) version 23.0 thesaurus.

A treatment-related AE is any AE with a relationship to the study drug of possibly, probably, likely, or missing.

For partial AE and medication start dates:

- If the year is unknown, then do not impute the date but assign a missing value.
- If the year is known, but the month or month and day is unknown, then:
 - If the year matches the year of first dose date and the end date (if present) is after first dose date, then impute as the month and day of the first dose date.
 - Otherwise, assign 01 January.
- If the year and month are known, but the day is unknown, then:
 - If the month and year match the month and year of the first dose date, then impute as the day of the first dose date.
 - Otherwise, assign 01.

For partial AE and medication end dates:

- If the year is unknown, then do not impute the date but assign as missing value.
- If the year is known, but the month or month and day is unknown, then:

- If the year matches the year of the last date of the study (date of last contact if subject lost to follow-up; date of completion or early termination otherwise), then impute as the month and day of the last date of the study.
- Otherwise, assign 31 December.
- If the year and month are known, but the day is unknown, then:
 - If the month and year match the month and year of the last date of the study, then impute as the day of the last date of the study.
 - Otherwise, assign the last day of the month.

These conventions will be applied to AE and medication onset dates and times with the following precaution: if the missing date and time reflect the date and time of onset of an AE, the modified date and time will be constructed to match the first documented date/time post drug administration while preserving the order in which the AE was reported in the eCRF.

In cases where variables for questionnaires were derived in the eCRF (e.g., total scores) and a derivation is indicated in Section 6.1.7, the results as derived by statistics (as opposed to the results derived in the eCRF) will be used in analysis.

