#### 5.1.10 Adverse Events

Adverse events (AEs) will be collected beginning at informed consent and assessed at the following visits and throughout the study:

Screening, Baseline, Weeks 2, 4, 8, and 9

Any treatment emergent AEs will be followed in the clinic for up to one month at the Investigator's discretion until resolved or otherwise judged as clinically stable.

For further details on Adverse Events please see [Section 5.7](#).

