- **CDLQI Score** = sum of the 10 questions (individual questions scored as Very much=3, Quite a lot=2, Only a little=1, Not at all=0; Question 7: if the last week was school time, the question was scored as Very much=3, Quite a lot=2, Only a little=1, Not at all=0, with Prevented school recoded to 3, and if the last week was vacation, the standard responses apply; range for score 0 to 30). If 1 item is missing, that item is scored as 0. If 2 or more items are missing, the score should not be calculated.

- **PSD Total score** = sum of the 16 questions (individual questions scored 0 to 10, where higher scores indicate more severe symptoms; range for total score 0 to 160). If 1 or more items are missing, the score is not calculated.
- **Compliance** = number of applications divided by the expected number of IP applications for each subject. Compliance will be calculated using drug accountability data over the entire treatment period for each subject, up to treatment completion or discontinuation.
 - **Number of expected IP applications** = 56 for subjects who complete the study or number of days between first and last application of IP (last treatment date - first treatment date + 1) for subjects who discontinue early from the study.
 - **Number of IP applications** = number of expected IP applications – missed IP applications as collected in the electronic case report form (eCRF).
- **Weight of IP (g)** = returned can weight – dispensed can weight.
- **Body mass index (BMI) (kg/m²)** = [weight (kg) / height (cm) / height (cm)] x 10,000.
- **BMI Categories**
 - Underweight: BMI < 18.5
 - Normal: 18.5 ≤ BMI ≤ 24.9
 - Overweight: 25.0 ≤ BMI ≤ 29.9
 - Obese: BMI ≥ 30.0
- **Change from baseline** = value at current time point – value at baseline.
- **Treatment emergent AE (TEAE)** = any AE with an onset date/time after the first application of IP.
- **PHQ-8** = sum of the 8 questions (individual questions scored as Not at all=0, Several days=1, More than half the days=2, and Nearly every day=3; range for score 0 to 24). If more than 1 item is missing, the score should not be calculated. If 1 item is missing, the score is calculated as (sum of answered items*8)/number of answered items.

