9.8. Concomitant Medication

Prior and concomitant medications will be summarized descriptively by treatment, Anatomical Therapeutic Chemical (ATC) Class Level 4, and Preferred Term using counts and percentages.

Prior medications will be presented separately from concomitant medications. Medications that started before the first application of IP will be considered prior medications whether or not they were stopped prior to the first application of study drug. Any medications continuing or starting after the first application of study drug will be considered to be concomitant. If a medication starts before the first application of study drug and continues after the first application of study drug it will be considered both prior and concomitant.

Medications will be coded using World Health Organization (WHO) Drug Global B3, version September 2019.

10. Changes from Planned Analysis

The following analysis populations have been added:

- The mITT population has been added to handle situations where a subject was unable to attend the Week 8 visit or discontinued from the study before the Week 8 visit due to COVID-19 disruptions;
- The SPRU4-ITT and SPRU4-mITT populations have been added to facilitate SI-NRS analysis on the ITT and mITT populations, respectively; and
- The PRU4-ITT and PRU4-mITT populations have been added to facilitate WI-NRS analysis on the ITT and mITT populations, respectively.

These populations are not included in the protocol.

The PP population and associated analyses have been removed at the request of the Sponsor, as they were considered to be uninformative.

Additional exploratory endpoints have been added in the SAP which are not specified in the protocol. They are:

- Change and percent change from baseline in SI-NRS at Weeks 2, 4, and 8
- Change and percent change from baseline in PASI at Weeks 2, 4, 8, and 9
- Change and percent change from baseline in WI-NRS at Weeks 2, 4, and 8

Additionally, odds ratios and 95% CIs of odds ratios for comparisons between treatment groups, and 95% Wilson CIs for proportion of successes in each treatment group for binary outcomes will be provided.

Additional efficacy analyses have been added in the SAP which are not specified in the protocol, as requested by the Sponsor. They are:

- Analysis of S-IGA success based on the following subgroups (both ITT and mITT populations, observed data only):
 - Topical corticosteroids – naïve subjects
 - Topical vitamin D derivatives – naïve subjects

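### SAP 6.1.8: an adverse event with start day missing, onset in the first-dose month and a recorded stop before dosing is given a start date after its stop and counted as treatment-emergent

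*SAP*

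**What the plan says.** SAP 6.1.8 has two branches for a partial start date in the period of first dose.

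- **Month unknown (or month and day).** The first-dose date is used on this condition: "If the year matches the year of first dose date and the end date (if present) is after first dose date". Otherwise the start becomes 01 January.
- **Only the day unknown.** "If the month and year match the month and year of the first dose date, then impute as the day"; the day meant is the one on which dosing began. In any other month the start becomes day 01. The end date is not mentioned.

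A closing precaution in the same section deals with missing adverse event onsets: "the modified date and time will be constructed to match the first documented date/time post drug administration", keeping the order in which events were reported in the eCRF. It has no end-date check either.

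Treatment-emergent status depends on onset alone. SAP 6.1.7 defines it as "any AE with an onset date/time after the first application of IP", SAP 9.1 uses a start after application at Baseline, and protocol 6.4.1 uses an onset on or after the date of study treatment.

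Events that are over before dosing can be in the database. Protocol 5.1.10 states: "Adverse events (AEs) will be collected beginning at informed consent". Protocol 4.3 allows up to 4 weeks between Screening and Baseline.

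The start-date branches also cover medications. SAP 9.8 says: "Medications that started before the first application of IP will be considered prior medications".

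**The concern.** The month-unknown branch recognises that a known stop date can show an event was over before treatment. The day-unknown branch has a more precise start date and ignores that evidence. Where the conditions meet, the rule produces a record that cannot be true, with a start later than its own stop, and assigns it to the treatment period.

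Safety is part of the primary objective, and the treatment-emergent event tables are a main output for it. A screening-period event should not appear there when the case report form itself shows it ended before the first application.

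**Working it through.** The plan has no figure to reproduce, so the check applies the written rules to dates.

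**Test case (dates illustrative).** First dose 20 February 2020; last study date 23 April 2020 (Day 63); event known to have stopped on 10 February 2020 except where the table says otherwise.

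| What is recorded | Imputed start | End date | Start after stop? | Onset on or after first dose? |
|---|---|---|---|---|
| Start day unknown, February 2020; stop 10 Feb | 20 Feb | 10 Feb | Yes, by 20 − 10 = 10 days | Yes |
| Start day and month unknown, 2020; stop 10 Feb | 01 Jan | 10 Feb | No | No |
| Start and stop days both unknown, February 2020 | 20 Feb | 29 Feb (imputed) | No | Yes |
| Start day unknown, January 2020; stop 28 Jan | 01 Jan | 28 Jan | No | No |

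Row 2 applies the branch without the closing precaution. Row 3 shows that the reversal needs a complete stop date: when the stop day is also missing, SAP 6.1.8 moves the end to month end (or to the last study date if the months match). Row 4 shows that an onset in an earlier month is handled correctly.

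**Is the row 1 event treatment-emergent?** Under protocol 6.4.1, yes, because Day 0 is on the date of study treatment. The closing precaution points the same way, since it places the onset after drug administration. SAP 6.1.7 alone leaves it open, because an untimed Day 0 onset is not clearly after the application. No definition looks at the stop date, so none of them rescues the record.

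**How much of the possible pre-dose period is exposed?** Take a first dose on each of the 366 days of 2020 and every event that starts and ends 1 to 28 days before it, with start day missing and end date complete.

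- Start/end pairs per first-dose date: 28 × 29 / 2 = 406.
- Total cases: 366 × 406 = 148,596.
- Cases moved to the first-dose day: 56,028, and 56,028 / 148,596 = 37.7%. All 56,028 have start after stop.
- The other 148,596 − 56,028 = 92,568 began in an earlier month and go to day 01.
- With an end-date condition added to the day-unknown branch, misplaced or reversed cases fall to 0.

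The 37.7% is conditional on a missing start day and weights all date combinations equally. It does not predict a frequency in this trial.

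**Medications.** A drug started and stopped before dosing within the first-dose month gets a Day 0 start. That is not before the first application, so the drug fails the SAP 9.8 prior definition. It is then either read as concomitant or falls in neither table. Set against the washouts in protocol Table 1, with dosing on day D of the month:

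- 8 or 12 weeks: start and compliant stop cannot both fall in the first-dose month.
- 4 weeks: the stop must be by day D − 28, so D must be 29 to 31 and the drug must start and stop within days 1 to 3.
- 2 weeks: only a drug newly started that month and stopped by day D − 14.

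A drug begun in an earlier month goes to day 01 and stays prior.

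**The case against.** The strongest defence is that treating an uncertain onset as treatment-emergent is the usual conservative choice, and that any error here adds events to the tables and hides none. The default is sound when onset could lie on either side of dosing. It does not cover an event whose recorded stop date shows it was over before dosing.

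A second defence is that such records should be rare and visible. Protocol 5.7.5 requires date and time of onset for each event. Protocol 7.4 plans a 100% quality check and edit checks before lock. Listing 16.2.7.1 shows start, stop and the treatment-emergent flag together. This bears on the size of the problem and largely stands. It does not repair the rule, because the reversal is created in derivation and not in the collected data.

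Three stronger readings are tempting, and the documents do not support them.

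- A reader might infer that any adverse event that began and ended before dosing is moved to Day 0. Three conditions are needed together: missing start day, onset in the first-dose month, and a complete stop date before dosing.
- A reader might infer that the closing precaution overrides every branch and so contradicts the day 01 and do-not-impute rules. That is only one reading. The sentence begins by applying the conventions and refers to reporting order, so it may only place a time for dates already on the dosing day. If it did override everything, the month-unknown event in row 2 would move after dosing too, and the contrast between the branches would disappear.
- A reader might infer that washed-out prohibited drugs will generally appear as on-study use. The Table 1 washouts leave only the narrow cases shown above.

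**Conclusion.** The day-unknown branch is wrong as written. For an adverse event meeting the three conditions, it creates a start after the stop and leads to a treatment-emergent count under protocol 6.4.1. That classification rests on 6.4.1 and the closing precaution; SAP 6.1.7 alone is ambiguous for an untimed Day 0 onset. The medication consequence is real but affects few drugs.

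The size is probably small, though the documents give no count of partial dates. Only safety and medication tables and listings are touched. The primary endpoint, the testing strategy and the power are not, and SAP section 9 plans no inferential safety tests. The change is worth making because the error is certain where the conditions hold and the correction costs almost nothing.

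**What to change.** In SAP 6.1.8, day-unknown branch for start dates: where month and year match first dose, impute the first-dose day only if the end date is missing or is on or after the first-dose date; otherwise assign day 01 of the month. On or after keeps an event that ended on Day 0 conservatively treatment-emergent.

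State also that the closing precaution does not apply to an adverse event whose recorded end date is before first dose. Without that, the precaution could still move the onset after dosing.

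The cost is one clause, one clarifying sentence and a line of code, with no new data. In the test case the imputed start becomes 01 February, before the 10 February stop, and the event is not treatment-emergent. The count of treatment-emergent events may fall slightly.

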6.2. Special Handling for COVID-19 Disruptions

In some cases, study visits will have to be delayed/not performed as a result of COVID-19 disruptions (e.g., sites were closed or subjects were under stay-at-home orders). Where possible, study sites may collect post-baseline data from subjects remotely by telephone, traditional mail, and/or email; this will be clearly documented in the source. If possible, sites should adhere to the protocol visit window for remote data collection.

Investigator assessments and subject questionnaires normally completed directly in the electronic patient reported outcomes (ePRO) tablet during on-site visits should be completed on the appropriate paper source documents. The following assessments/questionnaires are approved to be collected via telemedicine/remotely:

- WI-NRS/SI-NRS
- DLQI/CDLQI
- C-SSRS
- PHQ-8/PHQ-A
- Subject Local Tolerability
- PSD

The following assessments cannot be completed via telemedicine/remotely:

- S-IGA/B-IGA
- BSA
- Investigator Local Tolerability
- PASI/mPASI
- PSSI
- Subject Weight

Study visits and procedures must be followed per protocol whenever possible. Any specific changes in study conduct that deviate from the protocol should be communicated to the institutional review board and Sponsor. All protocol deviations which occurred as a result of COVID-19 disruptions (e.g., visits out of window, missed assessments, etc.) will be differentiated from other protocol deviations.

Subjects who were affected by COVID-19 disruptions by either missing their Week 8 visit or being discontinued before having a Week 8 visit due to COVID-19 related disruptions will be excluded from the mITT population, as described in Section 5.

7. Study Subjects and Demographics

7.1. Disposition of Subjects and Withdrawals

Disposition will include tabulations of the number of subjects randomized into each treatment group, the number of subjects who received treatment, subjects completing study, tabulated reasons for discontinuation from the study, including whether or not the subject did not complete the study due to COVID-19 disruption and reasons, and number of subjects in each analysis population. Disposition will be summarized for all subjects who were entered into database by treatment group and overall.

7.2. Protocol Deviations

The number of subjects with major protocol deviations and/or eligibility deviations will be summarized in categories by treatment group and overall for subjects in Safety population.

7.3. Demographics and Other Baseline Characteristics

Summary statistics for age, age category (12-17, ≥ 18), gender (including child-bearing potential), race, ethnicity, height, weight, percent BSA, BMI, and baseline disease characteristics (S-IGA, B-IGA, PSSI, SI-NRS, PSD total score, PASI, mPASI, WI-NRS, DLQI, and CDLQI) will be presented by treatment group and overall.

A summary of treatment history, including history of response, intolerance, or contraindication to topical corticosteroids and/or topical vitamin D derivatives, and psoriasis involvement on knees and/or elbows and genitalia will be provided.

For the continuous variables, the number of nonmissing values and the mean, SD, minimum, median and maximum will be tabulated.

For ordinal variables such as the S-IGA, B-IGA, SI-NRS, and WI-NRS, summary statistics including the mean, median, and range of the ordinal variable will be presented, as well as frequency counts of each level of the ordinal variable.

For the categorical variables, the counts and proportions of each value will be tabulated.

These analyses will be conducted for the ITT, mITT, and Safety populations, except for treatment history summary, which will only be summarized on the Safety population.

7.4. Exposure and Compliance

The number of IP applications by each subject based on diary data will be summarized using descriptive statistics appropriate for continuous variables.

The amount of IP each subject used based on can weight will be summarized descriptively by treatment group using continuous methods.

A subject will be considered compliant with the dosing regimen if the subject applies at least 80% of the expected applications during the IP application period and does not miss more than 3 consecutive doses.

Investigational product application compliance will be calculated based on number of applications divided by the expected number of IP applications. Compliance will be summarized descriptively by treatment group using the following categories:

- >100%
- ≥80% - ≤100%
- <80%

8. Efficacy Analysis

The order of testing for the primary and secondary endpoints is discussed in Section 6.1.3. Exploratory endpoints are not included in the testing strategy.

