#### **6.1.7 Investigational Product Compliance**

The number of IP applications by each subject based on diary data will be summarized using descriptive statistics.

The amount of IP used by each subject based on can weight will be summarized by treatment using summary statistics (mean, SD, median, minimum, and maximum), and categorically.

IP compliance will be calculated based on number of applications divided by the expected number (amount) of IP for each subject. Compliance will be summarized descriptively by treatment group.

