Listing 16.2.5.3
 Diary Dispensation
 All Subjects

Subject ID	Treatment Received	Diary Dispensation Visit	Diary Dispensed?	Date Dispensed (Study Day)	Diary Returned Visit	Diary Returned and Reviewed?	Reason Diary not Returned	Date Returned (Study Day)
XXXXX	XXXXXX	XXXXXX	Yes	DDMMYYYY (X)	XXXXXX	Yes		DDMMYYYY (X)
		XXXXXX	Yes	DDMMYYYY (X)	XXXXXX	Yes		DDMMYYYY (X)
		XXXXXX	Yes	DDMMYYYY (X)	XXXXXX	No	XXXXXXXXXXXX	
XXXXX	XXXXXX	XXXXXX	No		XXXXXX	No	XXXXXXXXXXXX	

Note: Study day is calculated relative to the date of first application of study drug.

Listing 16.2.5.4
Compliance (CRF)
All Subjects

Subject ID	Treatment Received	Study Visit	Subject Compliant with Medication?	Date of Compliance Check (Study Day)	Compliance [1]	Overall Compliance [2]	Was Subject Retrained if not Compliant with Medication
XXXXXX	XXXXXX	XXXXXX XXXXXX XXXXXX	XXX XXX XXX	DDMMYYYY (X) DDMMYYYY (X) DDMMYYYY (X)	XX.X % XX.X % XX.X %	XX.X %	
XXXXXX	XXXXXX	XXXXXX XXXXXX XXXXXX	XXX XXX XX	DDMMYYYY (X) DDMMYYYY (X) DDMMYYYY (X)	XX.X % XX.X %	XX.X%	XXX

Abbreviations: IP = investigational product; CRF = case report form.

Note: Study day is calculated relative to the date of first application of study drug.

[1] This data comes from CRF page, unless otherwise specified.

[2] Overall compliance was calculated based on number of applications divided by the expected number of IP applications for each subject. Number of expected IP applications was calculated as number of days between first and last application of IP (last treatment date - first treatment date + 1). Number of IP applications was calculated as number of expected IP applications - missed IP applications as collected in the CRF.

Programming note: Populate overall compliance only for the first visit.

Listing 16.2.5.5
 Missed Doses
 All Subjects

Subject ID	Treatment Received	Study Visit	Date of Missed Dose (Study Day)	Missed Dose due to COVID-19 Disruption?	Reason for Missed Dose
XXXXXX	XXXXXX	XXXXXX XXXXXX	DDMMYYYY (X) DDMMYYYY (X)	No No	XXXXXXXXXXXXXXXXXX XXXXXXXXXXXXXXXXXX
XXXXXX	XXXXXX	XXXXXX	DDMMYYYY (X)	Yes	XXXXXXXXXXXXXXXXXX
XXXXXX	XXXXXX	XXXXXX XXXXXX	DDMMYYYY (X) DDMMYYYY (X)	No No	XXXXXXXXXXXXXXXXXX XXXXXXXXXXXXXXXXXX

Abbreviation: COVID-19 = novel coronavirus disease-19.

Note: Study day is calculated relative to the date of first application of study drug.

Programming note: Only subjects with missed doses should be presented in this listing.

Listing 16.2.5.6
 Pharmacokinetic Blood Collection

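### Compliance is derived by subtracting recorded missed doses, so it cannot exceed 100% and counts undocumented doses as applied

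*SAP*

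**What the plan says.** SAP 7.4 sets the ratio: "Investigational product application compliance will be calculated based on number of applications divided by the expected number of IP applications". It plans three categories: above 100%, 80% to 100%, and below 80%. A subject is compliant at 80% or more with no run of more than three missed doses. Table 14.1.6 repeats the categories and adds a row for compliant subjects.

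SAP 7.4 also gives a source for the count: "The number of IP applications by each subject based on diary data will be summarized using descriptive statistics". SAP 6.1.7 names a different one: "Compliance will be calculated using drug accountability data over the entire treatment period for each subject". It then derives the count without using either source directly, as "number of expected IP applications – missed IP applications as collected in the electronic case report form (eCRF". The footnote to Listing 16.2.5.4 confirms this: "Number of IP applications was calculated as number of expected IP applications - missed IP applications as collected in the CRF".

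The denominator in SAP 6.1.7 is "56 for subjects who complete the study or number of days between first and last application of IP", the second part being for subjects who discontinue early.

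Listing 16.2.5.3 foresees missing diaries, with a column headed "Reason Diary not Returned". Neither document says how to score such an interval.

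On the amount used, Protocol 6.1.7 says that IP use "based on can weight will be summarized by treatment using summary statistics (mean, SD, median, minimum, and maximum), and categorically". SAP 7.4 keeps only the continuous summary, and SAP Section 10 does not list the change.

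**The concern.** The categories in SAP 7.4 presuppose a count of applications that can fall below or rise above the expected number. The derivation in SAP 6.1.7 makes no such count, with two consequences.

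First, the top category is empty by construction. A printed zero in that row says nothing about over-application, but nothing in the table tells the reader so.

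Second, the absence of a record is treated as evidence of use. A dose counts as applied unless someone enters it as missed. Where diaries are missing, the total number of applications and the number of compliant subjects are pushed upward. Visits disrupted by COVID-19, which SAP 6.2 anticipates, are a plausible setting for such gaps.

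The protocol's categorical can-weight summary could have served as a cross-check. It was dropped without being declared.

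**Working it through.** **Inputs.** E is the number of expected applications and M the number of missed doses in the eCRF, with M ≥ 0 (both SAP 6.1.7). The 80% threshold and the three-dose rule are in SAP 7.4. The Week 8 visit window is ±5 days (Schedule of Events, both documents).

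**The plan's own figure.** Once daily for 8 weeks gives 8 × 7 × 1 = 56, which matches the stated 56.

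**The ceiling.** Compliance = (E − M)/E. With E = 56:

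- M = 0: 56/56 = 100%
- M = 11: 45/56 = 80.4%
- M = 12: 44/56 = 78.6%
- M = 28: 28/56 = 50%

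Because M cannot be negative, the maximum is 100%. This holds for any E, so it also covers early discontinuers and the footnote to Listing 16.2.5.4, which uses last minus first treatment date plus 1 without the 56-dose rule.

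**What a direct count would show.** The subjects below are hypothetical completers with no missed dose entered (M = 0) and, unless stated otherwise, daily use from Day 0.

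| Case | Documented applications / 56 | SAP 6.1.7 |
|---|---|---|
| Week 8 visit on Day 61, 61 applications | 61/56 = 108.9% | 100% |
| Week 8 visit on Day 51, 51 applications | 51/56 = 91.1% | 100% |
| Week 4 to 8 diary not returned, half of its 28 doses applied | 28/56 = 50% (actual use (28 + 14)/56 = 75%) | 100% |
| No diary after Week 2, product stopped at Week 2 | 14/56 = 25% | 100% |

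The first row shows that values above 100% can arise with once-daily use inside the visit window. In the third row, actual use is below the 80% threshold but the subject is reported as compliant. The fourth row assumes that the subject is a completer under SAP 6.1.7, which defines completion by the Week 8 S-IGA, and that this definition governs the 56-dose rule. If it does not, E = 14 and the score is 14/14, still 100%.

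**The second condition.** A subject with no missed dose entered also has no run of more than three missed doses. Both parts of the compliance definition are therefore met by default.

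**Would leaving out the missing intervals help?** No. Removing them from numerator and denominator gives 28/28 = 100% in the third row and 14/14 = 100% in the fourth.

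**The case against.** The strongest reply is that M comes from the eCRF and not from the diary alone. Protocol 4.6.4 has site staff question subjects about compliance, and Listing 16.2.5.5 holds dated missed doses with a COVID-19 flag. A site can therefore enter missed doses without a diary. Moreover, the schedule footnotes in both documents say that the compliance calculation is described in the IP Handling Manual, which is not available here and may contain a rule for missing diaries. A completer has also had a Week 8 S-IGA, which SAP 6.2 does not allow to be done remotely, at a visit that schedules diary review and kit weighing. This makes the COVID-19 argument weaker for completers.

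Much of this stands. A reader might infer that an unreturned diary always scores 100%. The documents do not say so; 100% is the formula's default when nothing is entered. A reader might also infer that over-use and under-use are hidden throughout. That goes too far: Table 14.1.6 gives total weight of IP with mean, SD, median, minimum and maximum, Listings 16.2.5.1 and 16.2.5.2 give can weights by subject, and Protocol 4.6.3 has sites compare actual with expected use for retraining. Protocol 6.1.7 does not specify a ratio of grams used to grams expected; it asks only for categories.

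None of this touches the ceiling. SAP 6.1.7 states its own derivation, the listing footnote repeats it, and no site practice can produce a value above 100% under it. Nor does a continuous summary of grams, not set against an expected amount, show which subjects used too much or too little.

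**Conclusion.** The point holds in limited form. The >100% row is a structural zero; this follows from the SAP text alone. The upward bias in the application count and the compliant count is conditional: it arises where a diary is missing and no missed doses are entered. Its size depends on how often that happens, which the documents do not give. For one subject with a missing Week 4 to 8 diary and otherwise full use, the true value can lie anywhere from 50% to 100%, while 100% is reported. The undeclared loss of the categorical can-weight summary is a plain difference between Protocol 6.1.7 and SAP 7.4.

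The consequence is confined to descriptive exposure reporting. A reader might suppose that efficacy results are affected. They are not: SAP Section 10 removes the per-protocol population, which was the efficacy population defined by the 80% rule, and the primary estimand in SAP 8.1.1 uses a treatment policy strategy on the ITT population. The correction is still worth making, because the exposure table supports the reading of both safety and efficacy and the present rule errs toward full compliance exactly where the record is missing.

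**What to change.** 1. In SAP 6.1.7 and 7.4, take the numerator from applications documented in the diary, which records the date and time of each dose (Protocol 4.6.4). The >100% category can then occur. If the subtraction rule is kept, delete that row. Name one data source in both sections, and align the denominator in the Listing 16.2.5.4 footnote with SAP 6.1.7.
2. Do not score an interval with no returned diary and no missed-dose entries as applied. In Table 14.1.6, report how many subjects have such an interval. Show compliance twice: with those doses counted as not applied (lower bound) and under the current rule (upper bound). Excluding the intervals is not enough, as the 14/14 and 28/28 cases show.
3. Restore the categorical can-weight summary of Protocol 6.1.7, or declare its removal in SAP Section 10. One option is categories relative to the BSA-expected use in the IP Handling Manual that Protocol 4.6.3 cites; the cut points would have to be set with that manual in hand.

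The cost is SAP wording and one table shell, with a footnote change in one listing. Diary return status, missed doses and can weights are already collected. The downside is a slightly longer table and less favourable compliance figures.
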